Important neurotransmitters involved in the carotid body response to hypoxia include acetylcholine, which acts through local nicotinergic acetylcholine receptors. Apart from the observation that muscle relaxants (which are blockers of the acetylcholine receptors) affect the proper functioning of the carotid bodies (see Eriksson et al. Anesthesiology 1993; 78: 693-9), we have no knowledge on the dynamic effects of muscle relaxants on carotid body function over time or on the relationship between carotid body function and Train-of-Four (TOF) ratio over time.* Additionally, there is no data on the link between the use of NMB antagonists and return of carotid body function. Linking TOF ratio to carotid body function is of clinical importance as a possible relationship will allow clinicians to predict carotid body function from the TOF ratio. The latter is highly relevant as we show in the Neuropa trial that a large proportion of patients is extubated at TOF ratio's < 0.7.

Apart from the carotid bodies, chemoreceptors in the brainstem exist that are sensitive to hypercapnia. This response system is not under control of cholinergic neurotransmission. Since we may assume that the hypercapnic ventilatory response is not influenced by muscle relaxants we can use this response to calibrate the hypoxic ventilatory response as both responses are equally affected by the effect of muscle relaxants on muscle function (Eriksson et al. Anesthesiology 1993; 78: 693-9).

As stated there is data on the effect of muscle relaxants on carotid body function at one fixed TOF ratio (TOF ratio fixed at 0.7; Eriksson et al. 1993). No data are available on:

* TOF is a measure of muscle relaxation and is the response to 4 stimuli to the ulnar nerve. A moderately relaxed patient has no TOF responses (TOF = 0); Absence of muscle relaxation gives a TOF of 4. A very mild muscle block is observed by “fading” in which the strength of the 4 stimuli decreases. We can then calculate a TOF ratio. In the current study we will apply TOF ratios of 0.6 or greater, which indicate mild muscle relaxation.

1. Dynamic effect of carotid body function as measured by the hypoxic ventilatory response at TOF ratio's slowly changing from 0.6 to 1.0;
2. Dynamic effect of reversal of NMB by sugammadex versus neostigmine.

Sugammadex and neostigmine are both reversal agents of neuromuscular blockade. At LUMC we use both agents in clinical practice but remain without knowledge on their effects on carotid body function. Our current proposal is designed to study items 1 and 2 in healthy awake volunteers.

2. Study objectives

To assess (i) the effect of partial neuromuscular blockade (NMB; TOF ratio 0.8 and 0.6) induced by low-dose rocuronium on the ventilatory response to isocapnic hypoxia and (ii) the effect over time (from TOF 0.6 to TOF 1.0) of the reversal by sugammadex, neostigmine or placebo in healthy volunteers.

To assess the effect of partial NMB (TOF ratio 0.6) induced by low-dose rocuronium on the ventilatory response to hypercapnia and effect over time (from TOF 0.6 to TOF 1.0) of the reversal by sugammadex, neostigmine or placebo in healthy volunteers.

3. Hypotheses

- A. Rocuronium will induce impairment of carotid body function through blockade of cholinergic neurotransmission in carotid bodies resulting in a reduced or absent ventilatory response to isocapnic hypoxia.
- B. Sugammadex will completely restore carotid body function following rocuronium administration with full reversal of the ventilatory response to isocapnic hypoxia within 2 min.
- C. Neostigmine will cause a protracted reversal of the carotid body function following rocuronium administration with full reversal within 40-60 min.

4. Volunteers

We will study 30 healthy male volunteers. They will be randomized to receive low-dose rocuronium followed by one of three reversal treatments: placebo (normal saline), neostigmine (1 mg) or sugammadex (2 mg/kg). All volunteers will receive a physical examination prior to enrollment.

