4.5 Pre-study requirements

All subjects will be asked to refrain from food 6 hours prior to the study and from drinks 2 hours prior to the study.

5. Study design

This is a randomized, double blind, 3-arm, placebo controlled parallel study on the influence of reversal of a partial NMB on carotid body function following rocuronium administration. Healthy volunteers will be randomized to receive either placebo (Group1, n = 12), neostigmine (1 mg, n = 12) or sugammadex (2 mg/kg, n = 12) following a continuous rocuronium infusion for 120 min aimed at a TOF ratio of 0.8 for 1 h followed by 0.6 for another hour. Prior to the rocuronium infusion and during the infusion, ventilatory responses to isocapnic 2-min hypoxic pulses will be obtained as well as the (hyperoxic) ventilatory response to hypercapnia. After the 120 min infusion and the administration of reversal agents, the ventilatory response to hypoxic pulses will be obtained at 5 min interval for at least 60 min. In case the response has not returned to pretreatment control values, additional responses will be obtained. Hereafter, a final ventilatory response to carbon dioxide will be obtained (at hyperoxic conditions).

All procedures will be executed in compliance with the current revision of the Declaration of Helsinki and Good Clinical Practice guidelines. The trial starts after the medical ethical committee has approved the study protocol and will have a maximum duration of one year.

5.1 Rocuronium administration:

We will titrate rocuronium to effect followed by a target controlled infusion aimed at a TOF ratio of 0.8 and 0.6 (see Fig. 1). After 120 min the continuous infusion will be terminated. The plasma concentration and expected TOF ratio is simulated in Figure. 1.

[figure not shown]

Figure 1. Simulated plasma concentration (LEFT) and expected TOF ratio (RIGHT). A continuous infusion of rocuronium for 120 min (1st hours aimed at TOF ratio 0.8, 2nd hour TOF ratio 0.6). Additionally during the 1 hour period after reversal the timing of hypoxic challenges are given (vertical dotted lines).

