7.1 Data analysis

We will obtain HVR and S under control conditions (HVRc and Sc) and under rocuronium conditions at TOF 0.6 (HVRr and Sr). The ratio of HVRr/HVRc and Sr/Sc will be calculated. This will give an indication of the effect of rocuronium on respiratory muscles per se ($\text{Sr/Sc} = S'$) and on the combined effect of rocuronium on respiratory muscles and carotid bodies ($\text{HVRr/HVRc} = \text{HVR}'$). To compute the effect of rocuronium on just the

carotid bodies F' is calculated which is the ratio of HVR'/S' . In other words the effect of rocuronium on hypercapnic ventilation is used to correct for the effect of rocuronium on respiratory muscles (as well as other influences such as drowsiness, discomfort, etc). A value of $F' < 1$ is the effect of rocuronium on the carotid bodies. See also Eriksson et al. 1993.

The dynamics of return of the HVR towards control values following reversal is our main end-point. We are aware that the absolute value of the HVR is contaminated by effects from the respiratory muscles next to an effect of rocuronium at the carotid bodies. However, the calculation made on HVR and S obtained before and during rocuronium infusion give us an indication on the distribution of muscle vs. carotid body effects. We will take this into account in our analysis. The HVR-time data will be analyzed by taking time, HVR and TOF ratio into account. This HVR-time data will be analyzed using an exponential function allowing assessment of a half-life for HVR return (and hence for return of carotid body function). The HVR-TOF ratio data will be analyzed by linear regression and allows assessment whether HVR return follows TOF ratio or whether it deviates from the TOF ratio.

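### A fitted HVR-TOF line would not by itself support predicting an individual's response from the TOF ratio, and the plan has no measure of individual spread

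*Combined protocol and SAP*

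**What the plan says.** The background gives the clinical reason for linking TOF to carotid body function: "a possible relationship will allow clinicians to predict carotid body function from the TOF ratio". It adds that this matters because many patients are extubated at TOF ratios below 0.7. The first gap the study sets out to fill is HVR at "TOF ratio's slowly changing from 0.6 to 1.0".

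Section 7.1 contains the one analysis of that link: "The HVR-TOF ratio data will be analyzed by linear regression and allows assessment whether HVR return follows TOF ratio", the alternative being that it departs from it. The section mentions no prediction interval, residual SD, between-subject SD or validation, and no method for repeated points within a subject.

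The same section says: "The dynamics of return of the HVR towards control values following reversal is our main end-point". Section 7.2 powers the study on speed of reversal, sugammadex against neostigmine. Prediction from TOF is not among the objectives (section 2) or hypotheses (section 3).

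**The concern.** A clinician with a TOF reading wants to know how far the patient in front of them may lie from the average. A slope, its p-value and its confidence band describe the average subject, and the band narrows as subjects and tests are added. The scatter of individuals around the line does not shrink. A steep, precisely estimated line is therefore compatible with some subjects at a TOF ratio near 1.0 whose hypoxic response is still well below control.

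At stake is the step the background takes from a relationship to its clinical use. The planned analysis can show the relationship. Without a measure of individual spread it cannot show that the relationship is close enough to use for one patient, and the intended use bears on safety at extubation.

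**Working it through.** **The plan's own figure.** The documents give no precision for the HVR-TOF regression, so there is none to reproduce. The one sample-size figure, 12 per group with power above 90% (section 7.2), concerns speed of reversal. It can be reproduced under one reading: a difference of 10 - 5 = 5 min and a per-arm SD of 5/√2 = 3.54 min give 12 per group and 91.1% power by two-sided t test. It has no bearing on this point.

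**Inputs.**
- Subjects: section 4 says "We will study 30 healthy male volunteers"; section 5 lists three groups of 12, which is 36. Both are used.
- TOF range: 0.6 to 1.0 (background and section 2).
- Tests per subject after reversal: section 5 says "the ventilatory response to hypoxic pulses will be obtained at 5 min interval for at least 60 min", so about 60/5 = 12.
- Assumptions, not in the documents: TOF values evenly spread over the range; the intra-subject correlation (ICC), varied from 0 to 1; the SD of HVR/HVRc at a given TOF, which cancels in the ratio below.

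**Formula.** In simple linear regression with residual SD s, the 95% half-width at TOF x₀ is t·s·√h for the mean and t·s·√(1+h) for a new individual, where h = 1/n + (x₀ - x̄)²/Sxx. The ratio of the two is √((1+h)/h), which at x₀ = x̄ reduces to √(n+1).

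**One independent point per subject.** For n evenly spaced values, Sxx = (0.4/(n-1))²·n(n²-1)/12. This is 0.428 for n = 30 and 0.507 for n = 36, with x̄ = 0.8.

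| TOF | h, n = 30 | ratio, n = 30 | h, n = 36 | ratio, n = 36 |
|---|---|---|---|---|
| 0.8 | 0.0333 | 5.57 | 0.0278 | 6.08 |
| 0.7 or 0.9 | 0.0567 | 4.32 | 0.0475 | 4.70 |
| 0.6 or 1.0 | 0.1269 | 2.98 | 0.1066 | 3.22 |

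Within one arm, the ratio at mean TOF is √13 = 3.6 (n = 12) or √11 = 3.3 (n = 10).

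**Repeated tests.** With m = 12 tests per subject, the effective number of points is n·m/(1 + (m-1)·ICC). At mean TOF with n = 36:
- ICC 1: 36 points, ratio 6.08
- ICC 0.5: 432/6.5 = 66.5 points, ratio √67.5 = 8.2
- ICC 0, which is what pooling as independent assumes: 432 points, ratio √433 = 20.8

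With n = 30 the corresponding ratios are 5.57, 7.5 and √361 = 19.0.

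**Absolute size, for illustration only.** At mean TOF with n = 36, t(34) = 2.032. The half-widths are 2.032/6 = 0.339 SD for the mean and 2.032·√(37/36) = 2.060 SD for a new subject. If the SD of HVR/HVRc were 0.15 to 0.30, the mean would be known to ±0.05 to ±0.10 and a new subject to ±0.31 to ±0.62.

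**The case against.** The strongest reply is that the prediction sentence is conditional background motivation. Section 7.1 gives the regression a different purpose, to which regression is suited, and neither the main endpoint nor the powered comparison is affected. All of that stands, and it limits the weight of the point. It does not remove it, because the regression is the only planned analysis that could support the stated clinical use.

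Four stronger readings are tempting, and the documents do not support them.
- A reader might infer that the regression can yield nothing but a mean line. The same fit gives a residual SD from which prediction limits can be computed. The plan is silent on this; it does not rule it out.
- A reader might infer that the protocol offers the precision of the line as its accuracy for individuals. It nowhere says so and sets no such decision rule.
- A reader might take six-fold as a fixed property of the design. It is √(n+1), which holds only at mean TOF with one independent point per subject. The even spread is also an assumption. Section 7.2 expects recovery within 3-5 min on sugammadex, and tests come every 5 min, so that arm may supply few intermediate TOF values. If points cluster near 1.0, the ratio peaks there and is smaller at the low end.
- A reader might suppose that an interval for HVR/HVRc describes carotid body function. Section 7.1 itself says that HVR also carries respiratory-muscle effects, and it defines the hypercapnic slope S under rocuronium only at TOF 0.6. The muscle-corrected ratio F' therefore cannot be followed across the TOF range as planned.

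It is also fair to say that the remedy needs a subject-level model, so it overlaps with the handling of repeated measures. The overlap is partial: a subject effect corrects the standard errors of the line but does not produce an interval for a new person unless one is asked for.

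**Conclusion.** The point holds as a gap between the stated clinical use and the planned analysis. A clear slope would answer whether HVR follows TOF on average; it would not by itself support prediction for an individual. The confidence band for the mean is narrower than a new-subject prediction interval by about 3-fold at TOF 0.6 and 1.0, rising to about 6-fold at 0.8. This assumes 30 to 36 subjects, one independent point each and evenly spread TOF. Treating all repeat tests as independent raises the ratio at mean TOF to about 19 to 21. The documents supply no SD, so how wide the prediction interval would be in absolute terms is unknown. The primary comparison and its sample size are untouched. The 30-versus-36 discrepancy barely affects this point but needs reconciling.

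**What to change.** In section 7.1, specify that HVR/HVRc is modelled on TOF ratio with a subject effect. Beside the 95% confidence band, report the 95% prediction interval for a new subject at TOF 0.7, 0.8, 0.9 and 1.0. Its variance should add the uncertainty of the line, the between-subject variance and the within-subject variance.

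State that any claim about prediction for an individual rests on this interval and not on the slope or its p-value. State also that it is prediction of HVR, not of carotid body function alone, and that it applies to healthy awake men over the TOF range studied. The alternative is to reword the background so that the rationale concerns the average relation only.

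The cost is a small amount of analysis on data already planned, with no extra subjects or tests. The clinical claim may come out weaker.

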5.2 Reversal

At $t = 120$ min, all subjects will receive a reversal agent which is placebo (NaCl 0.9%) for Group 1, neostigmine 1 mg/atropine 0.5 mg for Group 2 and sugammadex 2 mg/kg for Group 3.

[figure not shown]

Figure 2. Examples of hypercapnic (left and middle) and hypoxic challenges in a healthy volunteer. From Dahan et al. Anesthesiology 1994.

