After approval of the protocol by the Human Ethics Committee a total of 30 volunteers will be recruited and tested in the Clinical Research Unit of the Department of Anesthesiology at Leiden University Medical Center. Each volunteer will undergo a physical examination first and only healthy volunteers without a (family) history of neuromuscular disease will be included in the study.

The subjects are not allowed to eat or drink for at least 8 hours before the experiment.

After arrival in the laboratory all subjects will be connected to monitors including ECG, pulse oximeter and two EMG electrodes to measure diaphragmatic EMG activity; next an iv line is placed. The subjects are comfortably seated in a semirecumbant position. Next, the control ventilatory responses are obtained. A facemask will be used to administer specific gas mixtures.

Following the control ventilator responses and after a short break the rocuronium will be titrated to a TOF ratio of 0.8 for 1 hour followed by 0.6 for the next hour. In case the TOF ratio of 0.6 has a large effect on the subject in terms of oxygen saturation (values < 94%) or increases in end-tidal $\text{PCO}_2 > 9 \text{ kPa}$, we will increase the TOF ratio to 0.7 and if this has no effect to 0.8. The experiment is then continued. After the desired TOF ratio is reached, the ventilatory challenges are repeated. The TOF ratio will be measured with the TOF Cuff/TOF watch device at 25 mA. We know from experience that this is an acceptable current.

After the 120-min infusion, the subject is reversed with either placebo (normal saline), or neostigmine 1 mg, or sugammadex 2 mg/kg. We will then repeat the 2-min hypoxic challenges at 5 min interval. When the hypoxic response has returned to control values but not before 60 min have elapsed since reversal we will perform one final hypercapnic ventilatory response.

We expect that all values will normalize within 90 min. The iv line is then removed and after another break of 1 hours (observation period) the subjects is discharged.

The duration of one single experiment is about 4 hours (incl. post experiment observation period). The complete study requires 30 experiment days and will last about 6 months (incl. data analysis)

7. Data and sample size calculation

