7.2 Sample size calculation

We decided not to use a crossover design as we do not want to expose one person to multiple awake rocuronium infusions. Hence we chose a parallel design. We powered the study on the speed of reversal of HVR from TOF ratio 0.6 to TOF ratio 1.0 between sugammadex and neostigmine. Assuming a return of carotid body function within 3-5 min for sugammadex and at least 10-20 min for neostigmine with a SD of the difference of 4-5 min we calculate the need for 12 subjects per group giving a power of > 90% ($\alpha = 0.05$). The power calculation was performed in SigmaPlot.

8. Monitoring

The subject will be closely monitored by measurement of the TOF ratio using the TOFF Cuff/TOF watch system, oxygen saturation, respiratory rate, tidal volume, and ECG. In case of an emergency sugammadex will be administered to overcome the muscle blockade.

9. Subject discomfort

Due to the mild level of relaxation some subjects may experience some muscle weakness and dysarthria. This is frequently seen in postoperative patients and is well accepted, especially when subjects are well coached during the period of mild muscle relaxation. In case the subject indicates that his discomfort is unacceptable the level of

relaxation will be reduced, as discussed in paragraph 6. In case the subjects demands termination of the study the reversal agent Sugammadex will be administered.

There are multiple studies on the use of muscle relaxants in volunteers, such as the Eriksson et al. (1993) study. Here we give some examples:

Schuller et al. **Response of bispectral index to neuromuscular block in awake volunteers.** Br J Anaesth 2015; 115: i95-i103: Rocuronium 0.7 mg/kg was administered causing full paralysis in unsedated volunteers.

Blokland et al. **Detection of attempted movement from the EEG during neuromuscular block: proof of principle study in awake volunteers.** Sci Rep 2015; 5:12815: Complete relaxation in awake volunteers. Study performed at RadboudMC.

Cedbøg et al. **Pharyngeal function and breathing pattern during partial neuromuscular block in the elderly: effects on airway protection.** Anesthesiology 204; 120: 312-25: TOF ratios of 0.7 in elderly (>70 yrs) unsedated volunteers.

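### Hypothesis C credits neostigmine with a recovery time from its own arm, although rocuronium stops at the same moment and no stated analysis compares neostigmine with saline

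*Combined protocol and SAP*

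**What the plan says.** Section 3, Hypothesis C: "Neostigmine will cause a protracted reversal of the carotid body function following rocuronium administration with full reversal within 40-60 min". Hypothesis B takes the same form for sugammadex: "full reversal of the ventilatory response to isocapnic hypoxia within 2 min". Neither names a comparator.

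On timing, section 5.1 states "After 120 min the continuous infusion will be terminated", and section 5.2 states "At $t = 120$ min, all subjects will receive a reversal agent which is placebo (NaCl 0.9%) for Group 1", with neostigmine and sugammadex for the other two groups. The end of infusion and the reversal dose therefore coincide. Section 6 adds "We expect that all values will normalize within 90 min", with no exception for the saline arm.

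Section 5 describes the trial thus: "This is a randomized, double blind, 3-arm, placebo controlled parallel study". The objective in section 2 covers the effect over time "of the reversal by sugammadex, neostigmine or placebo in healthy volunteers". All arms have hypoxic challenges every 5 min for at least 60 min, with more if the response has not returned to control.

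Section 7.1 makes the course of HVR return the main end-point. It plans an exponential fit giving a half-life and a linear regression of HVR on TOF ratio. It names no between-arm comparison and does not mention placebo. Section 7.2 names one contrast: "We powered the study on the speed of reversal of HVR from TOF ratio 0.6 to TOF ratio 1.0 between sugammadex and neostigmine".

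**The concern.** Once the infusion is off, the block wears off in every arm. The recovery time in the neostigmine arm is the drug's effect combined with that unaided recovery, and one arm alone cannot separate the two. Hypothesis C nevertheless words the observed time as something neostigmine causes.

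The one stated contrast does not close the gap. It compares neostigmine with a much faster agent, not with no agent. A large advantage for sugammadex says little about whether neostigmine does anything for carotid body function.

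At stake is the neostigmine part of objective (ii). A recovery of 40 to 60 min could be reported as neostigmine reversal when saline did as well. If the saline comparison is chosen only after the data are seen, the choice among half-life, recovery time and the HVR-TOF slope is post hoc.

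**Working it through.** **1. The plan's own figure.** Inputs from 7.2: 3-5 min for sugammadex, 10-20 min for neostigmine, SD 4-5 min, 12 per group, power above 90%, alpha 0.05. Assumed: two-sided test, SD read as the per-arm SD. With a difference of 10 − 3 = 7 min and SD 5:

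n per group = 2(1.960 + 1.282)² × 5² / 7² = 10.7, so 11 by the normal approximation.

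The two-sample t test needs 12, with power 0.906. The stated size reproduces, for sugammadex versus neostigmine only.

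**2. What that contrast can show.** Take sugammadex at 3-5 min (7.2). The neostigmine and saline times below are assumed.

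| Neostigmine (min) | Saline (min) | Neostigmine − sugammadex | Neostigmine − saline |
|---|---|---|---|
| 50 | 30 | 45 to 47 | +20 (slows) |
| 50 | 50 | 45 to 47 | 0 (no effect) |
| 50 | 70 | 45 to 47 | −20 (speeds) |
| 30 | 50 | 25 to 27 | −20 (speeds) |
| 70 | 50 | 65 to 67 | +20 (slows) |

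In the first three rows, one observed neostigmine time gives one and the same contrast with sugammadex under three opposite truths. Rows 2, 4 and 5 hold saline fixed: the size of the contrast moves with neostigmine's effect, yet it favours sugammadex each time. Only the last column identifies the effect.

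**3. How readily Hypothesis C is met by an inert drug.** Let neostigmine do nothing, with recovery times normal with mean M and standard deviation SD, and 12 per arm. The arm mean has SE = SD/√12, and

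P(mean in 40-60) = Φ((60 − M)/SE) − Φ((40 − M)/SE).

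For M = 45 and SD = 15, SE = 4.33, and Φ(3.46) − Φ(−1.15) = 0.876. Simulation with 20,000 runs gives 0.873. Simulated results over SD 5, 10 and 15:

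| Assumed M (min) | P(arm mean in 40-60) |
|---|---|
| 30 | 0.00 to 0.01 |
| 40 | about 0.50 |
| 45 | 0.87 to 1.00 |
| 50 | 0.98 to 1.00 |
| 55 | 0.88 to 1.00 |
| 60 | about 0.50 |
| 70 | 0.00 to 0.01 |

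At M = 30 the mean misses the window only by being quicker: it was at or below 60 min in every run. In all these cases a neostigmine versus placebo t test is significant in about 5% of runs, as it should be. Every M and SD here is an assumption except SD 5, the top of the 7.2 range.

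**4. Precision of the missing contrast.** Difference detectable at 90% power, t test, two-sided 0.05. Both arm sizes are shown because section 5 gives 12 per arm while sections 4 and 6 give 30 in total, or 10 per arm if equal.

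| SD (min) | 12 per arm | 10 per arm |
|---|---|---|
| 4 | 5.54 min | 6.13 min |
| 5 | 6.93 min | 7.67 min |
| 10 (assumed) | 13.85 min | 15.34 min |
| 15 (assumed) | 20.78 min | 23.01 min |

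The documents give no SD for the saline arm, and the 7.2 values may not carry over to slower recovery.

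**The case against.** The strongest reply is that the design already contains the answer. Saline is randomised, blinded, given at the same moment and followed with the same challenges, and the half-life fit is not limited to the active arms. A reader may take the comparison as implied. The background also names sugammadex versus neostigmine as the knowledge gap, which the powered contrast matches. All of this stands. It confines the defect to the hypothesis and the analysis section; the data will be there. It does not supply a stated contrast with saline. The HVR-TOF regression does not supply one either, because TOF ratio also recovers unaided in every arm.

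Four stronger readings are tempting, and the documents do not support them.

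- A reader might infer that 40-60 min is a formal success rule. It is a prediction in section 3; section 7.1 sets no such criterion.
- A reader might infer that the sugammadex-neostigmine result is the same whatever neostigmine does. Its size changes with neostigmine's effect; its direction need not.
- A reader might extend the point equally to Hypothesis B. Unaided recovery is an unlikely explanation for full return within 2 min, so B is hardly exposed.
- A reader might set the 90 min in section 6 against Hypothesis C and conclude that the misattributed effect lies between 0 and 50 min (90 − 40 = 50, 90 − 60 = 30, or 0 if saline matches neostigmine). The 90 min is one pooled expectation with no arm named. If saline recovered before 40 min, the same result would mean slowing, which that range leaves out.

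**Conclusion.** The point holds for Hypothesis C. As written, the hypothesis can be met with no neostigmine effect, and the only contrast the plan states cannot attribute recovery to neostigmine. The neostigmine part of objective (ii) therefore has no stated analysis that answers it.

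The size cannot be fixed from the readable text, which gives no spontaneous recovery time for the saline arm (Figure 1 is not shown). The probability that an inert drug meets the 40-60 min window runs from almost nil to almost certain, depending on that time. Any numerical range for the misattributed effect is illustrative only.

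The conclusion itself needs no assumed number. It rests on three facts in the text: the infusion ends when the agent is given, Hypothesis C has no comparator, and sections 7.1 and 7.2 state no contrast with placebo. The design and the data to be collected are sound on this point.

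**What to change.** In sections 3 and 7.1:

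- Restate Hypothesis C as neostigmine versus placebo in HVR recovery: a difference or ratio of half-life or recovery time, with a confidence interval. Choose the measure in advance.
- Report sugammadex versus placebo in the same way, for completeness.
- Keep sugammadex versus neostigmine as the powered contrast, and state it in 7.1 as well.
- Report within-arm recovery times as description, and credit recovery to an agent only where it differs from saline.

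The cost is some wording and two further contrasts on data already planned, with no new subjects or procedures. The drawback is precision: the placebo contrasts have no stated power, and neostigmine versus placebo may be inconclusive if recovery times vary widely. The plan should say so, and should not read an inconclusive interval as proof that neostigmine has no effect.
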